#### Assess Impact of Stratification:

- 5) PFS using stratification factors as obtained from the baseline CRF pages (instead of IRT). The hazard ratio associated with treatment will be presented along with the associated two-sided 98% CIs. This analysis will be performed only if at least one stratification variable/factor at randomization (as per IRT) and baseline are not concordant for at least 10% of the PD-L1 CPS  $\geq 5$  randomized subjects for the 2 arms.
- 6) PFS using an un-stratified log-rank test. The hazard ratio associated with treatment will be presented along with the associated two-sided 98% CIs.
- 7) PFS using an unstratified Cox proportional hazards model, adjusted, using as covariates only the stratification factors used in randomization. The hazard ratio associated with treatment will be presented along with the associated two-sided 98% CIs.

#### PFS using different sources or definition:

- 8) PFS by BICR using secondary definition of PFS (ITT) will be compared between nivo+chemo vs. chemo, using a two-sided log rank test, stratified by the stratification factors as specified in [Table 7.5-1](#). In addition, for PFS by BICR using secondary definition, PFS using the investigator's assessment the primary definition and PFS using investigator's assessment and the secondary definition the hazard ratio associated with treatment with its 98% CI. The PFS function for each treatment group will be estimated using the KM product limit method and will be displayed graphically. A two-sided 95% CI for median PFS in each treatment group will be computed via the log-log transformation method. PFS rates at fixed time points (eg, 6, 12, 18 months, depending on the minimum follow-up) will be presented along with their associated 95% CIs. These estimates will be derived from the Kaplan Meier estimate and corresponding CIs will be derived based on Greenwood formula for variance derivation and on log-log transformation applied on the survivor function.

A by-subject listing will be presented including treatment group, PFS duration under the primary definition, PFS duration on the ITT definition (secondary definition), whether the subject was censored under the primary definition, and if censored, the reason, and whether the subject was censored under the ITT definition, and if censored, the reason.

- 9) A cross tabulation of PFS assessment by BICR versus PFS assessment by investigator will be presented, by treatment group. The concordance rate of events will be computed as the frequency with which investigator and BICR agree on classification of a subject as progression

vs. death vs. censored as a proportion of the total number of randomized PD-L1 CPS  $\geq 5$  subjects assessed by both the investigator and BICR.

A by-subject listing of PFS (primary definition) assessment per BICR and investigator will be presented.

Assessment of PFS in case of relevant protocol deviation:

- 10) If there are more than 10% PD-L1 CPS  $\geq 5$  randomized subjects with relevant protocol deviations the PFS (BICR primary definition) analysis will be conducted on subjects with no relevant protocol deviations. The hazard ratio associated with treatment will be presented along with the associated two-sided 98% CIs.
- 11) The stratified log rank test will be repeated on PFS (BICR) primary definition based on the first 228 events among the first 298 randomized subjects with CPS  $\geq 5$ . The hazard ratio associated with treatment with its 98% CI will also be provided. This analysis will reflect the primary analysis per original design (see Amendment 23).
- 12) PFS accounting for two or more consecutively missing disease assessments prior to PFS event: This analysis will be performed only if at least 10% of PFS events have missing prior disease assessments. In case a subject has two or more consecutively missing disease assessments, the subject will be censored at the last disease assessment date prior the PFS event.
- 13) Analysis in which progression-free subjects who are lost to follow-up for any cause will be considered as having an event at the time of the last tumor assessment date prior to loss to follow-up. This analysis will be performed only if at least 10% of the progression-free subjects are lost to follow-up.

### **7.5.2.3 Subset Analyses of Progression-Free Survival**

The influence of baseline and demographic characteristics on the treatment effect among randomized CPS  $\geq 5$  subjects will be explored via exploratory subset analyses. The median PFS (primary definition) based on KM product-limit method along with two-sided 95% CIs will be produced for the following subgroups:

- Region (Asia vs US vs. RoW; from CRF)
- Region (Asia [without China] vs. US vs. RoW [including China])
- ECOG performance status (0 vs. 1; from CRF)
- Age category (< 65,  $\geq 65$  and < 75,  $\geq 75$ ,  $\geq 65$ )
- Gender (male, female)
- Race (Asian, White, Other)
- Primary tumor location at initial diagnosis (GC, GEJ cancer, Esophageal Adenocarcinoma)
- Disease stage at initial diagnosis (Stage I-II, Stage III, Stage IV)
- Disease status (locally recurrent/advanced, metastatic)
- Prior surgery related to current cancer (yes/no)
- Prior radiotherapy (yes/no)
- Lauren classification (intestinal type, diffuse type, mixed, unknown)
- WHO histologic classification presence of signet ring cell (yes/no)
- TNM classification Metastasis (M0, M1, unknown/Mx)
- At least one target lesion (yes/no)

- Number of organs with baseline lesion (target or non-target;  $\leq 1$ ,  $\geq 2$ ) outside primary location (gastric, gastroesophageal junction and esophagus)
- Time from Initial Disease Diagnosis to Randomization (< 6 months, 6 months -< 1 year,  $\geq 1$  year)
- Peritoneal metastases (yes/no)
- Liver metastases (yes/no)
- H.pylori (no, yes, unknown)
- HER-2 status at study entry (negative, positive, unknown)
- Baseline albumin (< LLN,  $\geq$  LLN)
- Microsatellite instability (MSI-H, MSS, invalid, unknown)

A forest plot of the PFS unstratified hazard ratios (along with the 95% CIs) will be produced for each level of the subgroups listed above. The unstratified analysis comparing treatment (ie, Hazard Ratio) will be conducted if the number of subjects in the subgroup category is more than 10.

#### **7.5.2.4 Analysis of Overall Survival**

OS in randomized CPS  $\geq 5$  subjects will be compared between nivo+chemo vs. chemo at the interim and final analyses, using stratified log-rank test, stratified by the stratification factors as specified in [Table 7.5-1](#). An O'Brien and Fleming  $\alpha$ -spending function will be employed to determine the nominal significance levels for the interim and final analyses (see [Table 7.5.1-1](#)). The stratified hazard ratio between the treatment groups will be presented along with 100\* (1 -  $\alpha$ )% CI (adjusted for interim) and will be calculated using a stratified Cox proportional hazards model, with treatment as the sole indicator covariate (for the nivo+chemo and chemo arm). Ties will be handled using the exact method.

OS will be estimated using the KM techniques. A two-sided 95% CI for median OS in each treatment group will be computed via the log-log transformation method. OS rates at fixed time points (eg, 12, 18, 24, 36 months, depending on the minimum follow-up) will be presented along with their associated 95% CIs. These estimates will be derived from the Kaplan Meier estimate and, corresponding CIs will be derived based on Greenwood formula for variance derivation and on log-log transformation applied on the survivor function.

The status of subjects who are censored in the OS KM analysis will be tabulated for each treatment group using the following categories:

- On-study (on-treatment, in follow-up)
- Off-study (lost to follow-up, withdraw consent, never treated)

A by-subject listing will be presented including treatment group, first and last dose date, whether the subject died, and if censored, the reason, event/censored date and OS duration.

### 7.5.2.5 Supportive Analyses of Overall Survival

Sensitivity analyses to examine assumptions of the stratified Log-rank test and Cox model:

- 1) To examine the assumption of proportional hazards in the Cox regression model, in addition to treatment, a time-dependent variable defined by treatment by time interaction will be added into the model. If the two-sided Wald Chi-square p-value of the treatment by time interaction is less than 0.1 or if a visual examination of the K-M plot of the OS indicates a delayed separation of the curves, the following analyses and potential other exploratory analyses will be conducted in order to report the treatment effect when taking into consideration of the delayed effect.
  - a) Delayed effect of immunotherapy interventions may cause a late separation in the OS KM curves and non-proportional hazards. OS will be compared between treatment groups via a 2-sided max-combo test. The max-combo test statistic is the maximum of 4 different Fleming-Harrington family weighted log-rank test statistics.  $Z_m = \max(FH(0, 0), FH(0, 1), FH(1, 0), FH(1, 1))$ , where  $FH(\rho, \gamma)$  are the test statistics from the Fleming-Harrington family of test statistics.  $FH(0, 0)$  corresponds to the log-rank test, while  $FH(0, 1)$  is more sensitive to late-difference alternatives,  $FH(1, 0)$  is more sensitive to early difference with decreasing treatment effect and  $FH(1, 1)$  uses weights at the median.
  - b) The estimates of the OS hazard ratios will be estimated in 2 periods. The periods will be defined by a cut-off point. The optimal cut off point will be calculated using a stratified time-dependent Cox model with effects for treatment and period-by-treatment interaction. The optimal cut-off point will be estimated using a grid of possible cut off points and obtained by maximizing the partial log likelihood. Ties will be handled using the exact method. A two-sided 95% CI for the hazard ratio's will also be presented.
- 2) The method of Gail and Simon will be used to test for a qualitative interaction between treatment and strata. This test will be conducted at  $\alpha=0.10$  level. The p-value reported from this specific analysis is for descriptive purposes alone.

Assess impact of Potential Prognostic Factors on Treatment Effect:

- 3) A multivariate Cox regression model will be used in order to estimate the treatment effect after adjustment for possible imbalances in known or potential prognostic factors. The factors used in the randomization will be included in the model as stratification factors. However, all additional factors will be incorporated as covariates. The additional factors, which are all measured at baseline, will include the same factors as in the PFS analysis.

The level of the covariate normally associated with the worst prognosis will be coded as the reference level. The hazard ratio associated with treatment and with each of the baseline covariates will be presented along with associated 95% CIs.

- 4) The identification of the primary population using PD-L1 CPS  $\geq 5$  was introduced close to accrual completion. Therefore the randomization was not stratified by PD-L1 CPS  $\geq 5$ . The overall study population was stratified by:
  - PD-L1 expression level (tumor cells) ( $\geq 1\%$  vs.  $< 1\%$  or indeterminate)
  - Region: Asia vs. US vs. RoW

- ECOG performance status: 0 vs. 1
- Planned chemotherapy regimen (XELOX vs. FOLFOX)

As  $CPS \geq 5$  is not a stratification factor, while pronounced imbalance is not expected due to the large sample size in this group, thorough review of data will be conducted and a sensitivity analysis may be conducted.

The distribution of baseline characteristics (demographics, disease characteristics and the stratification factors) between the two treatment arms will be inspected for potential imbalance in the subgroup of subjects with PD-L1  $CPS \geq 5$ .

The distribution of these characteristics will also be assessed between the PD-L1  $CPS \geq 5$  subgroup and the overall population, regardless of treatment.

If a pronounced imbalance between the treatment arms is observed for one or several factors (eg,  $\geq 10\%$  difference between the frequency of the treatment arms for any level of the categorical variables) a multivariate Cox regression model will be used in order to estimate the treatment effect after adjustment for those factors identified. The factors used in the randomization, will be included in the model as stratification factors and the factors identified with imbalance will be incorporated as covariates. For the purpose of fitting the multivariate model and easy interpretation of the results, any continuous variable identified will be dichotomized using a cutoff around median value and some sub-categories of a categorical covariate could collapsed due to small size of the sub-categories.

#### Assess Impact of Stratification:

- 5) OS using stratification factors as obtained from the baseline CRF pages (instead of IRT). The hazard ratio associated with treatment will be presented along with the associated two-sided  $(1 - \alpha)\%$  CIs. This analysis will be performed only if at least one stratification variable/factor at randomization (as per IRT) and baseline are not concordant for at least 10% of the randomized subjects.
- 6) OS using an un-stratified log rank test. The hazard ratio associated with treatment will be presented along with the associated two-sided  $(1 - \alpha)\%$  CIs.
- 7) OS using an unstratified Cox proportional hazards model, adjusted, using as covariates only the stratification factors used in randomization. The hazard ratio associated with treatment will be presented along with the associated two-sided  $(1 - \alpha)\%$  CIs.

#### Assessment of OS in case of relevant protocol deviation:

- 8) If there are more than 10% subjects with relevant protocol deviations the OS analysis for subjects with no relevant protocol deviations will be conducted. The hazard ratio associated with treatment will be presented along with the associated two-sided  $(1 - \alpha)\%$  CIs.
- 9) The OS analysis (stratified log rank) will be conducted based on the first 420 randomized subjects with PD-L1  $CPS \geq 5$  (see Protocol Amendment 23) and all events observed in this

population. The hazard ratio associated with treatment will be presented along with the associated two-sided  $(1 - \alpha)\%$  CIs.

- 10) The OS analysis (stratified log rank) will be conducted based on the original planned number of events (ie, first 354 deaths) observed among randomized subjects with  $CPS \geq 5$ . The hazard ratio associated with treatment will be presented along with the associated two-sided  $(1 - \alpha)\%$  CIs.

#### **7.5.2.6 Subset Analyses of Overall Survival**

The influence of baseline and demographic characteristics on the treatment effect among all randomized  $CPS \geq 5$  subjects will be explored via exploratory subset analyses. The median OS based on KM product-limit method along with two-sided 95% CIs will be produced for the same subgroups as in the PFS analysis (see [Section 7.5.2.3](#)).

A forest plot of the OS unstratified hazard ratios (along with the 95% CIs) will be produced for each level of the subgroups listed above. The unstratified analysis comparing treatment (ie, Hazard Ratio) will be conducted if the number of subjects in the subgroup category is more than 10.

#### **7.5.2.7 Current Status of PFS and OS Follow-up**

The extent of follow-up for survival, defined as the time between randomization date and last known alive date (for subjects who are alive) or death date (for subjects who died), will be summarized descriptively (median, min, max, etc.) in months for randomized  $CPS \geq 5$  subjects and all randomized subjects.

The currentness of follow-up for survival, defined as the time between last OS contact (ie, last known alive date or death date) and cutoff date (defined by last patient last visit date), will be summarized in months for randomized  $CPS \geq 5$  subjects and all randomized subjects. Subjects who died and subjects with last known alive date on or after data cut-off date will have zero value for currentness of follow-up.

Minimum follow-up of OS for all randomized subjects, defined as the time from cutoff date to last subject's randomization date, will be summarized in months.

Time from last evaluable tumor assessment to cut-off date in months will be summarized by treatment group and overall for randomized  $CPS \geq 5$  subjects and all randomized subjects. Subjects who have a PFS event will be considered as current for this analysis. The secondary definition of PFS will be used for this summary.

A by-subject listing will also be produced to accompany the subject time from last evaluable tumor assessment.

#### **7.5.2.8 Analysis of OS by Tumor Response:**

Survival by response category will be analyzed by arm using the landmark method. Subjects still on study at the landmark time will be separated into two response categories according to whether they have responded before that time. This will assess whether survival from the landmark depends

on the subject's response status at the landmark. Subjects who go off protocol (eg, subjects who die) before the time of landmark will be excluded from the analysis.

The survival curves from Week 6, Week 12, Week 18, Month 6, Month 9, Month 12, by response status, for each randomized arm will be produced using the KM product-limit method. Two sided, 95% CIs for median OS will be constructed based on a log-log transformed CI for the survivor function  $S(t)$ .

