5.4 Efficacy Assessments

Study evaluations will take place in accordance with the flow charts in Section 5.1. Baseline tumor assessments should be performed within 28 days prior to randomization, utilizing CT or MRI. In addition to chest, abdomen, and pelvis, clinically indicated sites as determined by the treating investigator should be assessed at baseline. Subsequent assessments should include all sites that were assessed at baseline and should use the same imaging method as was used at baseline. Subjects will be evaluated for disease progression every 6 weeks from the date of first dose (± 7 days) up to and including Week 48, and then every 12 weeks (± 7 days) thereafter, regardless of treatment schedule, until disease progression (unless treatment beyond PD is permitted; see Section 4.5.1.6), or the subject withdraws consent, whichever comes first. Subjects who discontinue study treatment for reasons other than PD will continue to have tumor assessments until their disease progresses or they withdraw consent.

Contrast-enhanced CT with PO/IV contrast or contrast-enhanced MRI are the preferred imaging modalities for assessing radiographic tumor response. If a subject has a known allergy to contrast material, local prophylaxis standards may be used to obtain the assessment with contrast if at all possible, or use the alternate modality. In cases where contrast is strictly contraindicated, a non-contrast scan will suffice. Should a subject have a contraindication for CT IV contrast, a non-contrast CT of the chest and a contrast enhanced MRI of the abdomen pelvis, and clinically indicated sites may be obtained. Every attempt should be made to image each subject using an identical acquisition protocol and the same method for all imaging time points.

Tumor measurements should be made by the same investigator or radiologist for each assessment whenever possible. Change in tumor measurements and tumor response will be assessed by the Investigator using the RECIST 1.1 criteria (Appendix 4). Correction: the Verification of Response stated in the Appendix 4.1.2 should be confirmation of PR and CR is required \geq 4 weeks to ensure that the responses identified are not the result of measurement error.

All radiologic imaging from this study will be transmitted to a centralized imaging core laboratory for Blinded Independent Central Review (BICR).

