### 4.1.2 Progression-Free Survival

Two definitions are used for analysis of Progression-Free Survival. The primary definition accounts for subsequent therapy by censoring at the last evaluable tumor assessment on or prior to the date of subsequent therapy. This definition will be used to run the primary analysis of PFS (per BICR) for this trial and to declare statistical significance for the PFS endpoint.

The secondary definition is irrespective of subsequent therapy and will be presented as supportive analysis of the primary PFS analysis. This definition is considered primary by EMA.

Clinical deterioration in the absence of unequivocal evidence of progression (per RECIST v1.1 criteria) is not considered progression for purposes of determining PFS.

PFS rates at fixed time points (eg, 6 months, depending on the minimum follow-up) are defined as the probability that a subject has not progressed and is alive at time  $T$  following randomization.

The first on-study tumor assessment is scheduled to be conducted at 6 weeks ( $\pm 1$  week) following first dose. Subsequent tumor assessments are scheduled every 6 weeks ( $\pm 1$  week) up to and including Week 48, then every 12 weeks ( $\pm 7$  days) regardless of treatment schedule until disease progression.

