##### **Time to objective response (BICR) in randomized CPS $\geq 5$ subjects and all randomized subjects.**

Time to response will be evaluated per BICR assessment. Summary statistics will be provided for each treatment group for subjects who achieve PR or CR. For these analyses the population is restricted to subjects with measurable disease at baseline.

To assess further tumor response kinetics, time to response will be analyzed using the KM methodology. Kaplan-Meier curve will represent the cumulative rate of response over time. For

the non-responders, time to response will be censored at the maximum time of response + 1 day of all subjects in their respective treatment group. Cumulative Response Rates will be tabulated for Week 6, Week 12, Months 4, 6, 8, and 12, and overall Response Rate will be provided for each treatment group.

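### The Week 6, 12 and 18 landmarks for survival by tumor response lie inside the scan windows, so some responses first seen at that scan are classed as non-response

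*SAP*

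**What the plan says.** SAP 7.5.2.8 (nivolumab plus chemotherapy) and SAP 7.5.3.4 (nivolumab plus ipilimumab) use the same landmark list: "The survival curves from Week 6, Week 12, Week 18, Month 6, Month 9, Month 12, by response status". At each landmark, subjects still on study are "separated into two response categories according to whether they have responded before that time", and subjects who have gone off protocol by then, for example through death, are excluded. The stated aim is to see whether later survival depends "on the subject's response status at the landmark". Output is Kaplan-Meier curves and medians within each arm, with no test. Neither section gives a grace period, the origin of the landmark clock, or the date on which a response counts.

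Protocol 5.4 schedules scans "every 6 weeks from the date of first dose (± 7 days) up to and including Week 48". From there the interval doubles to 12 weeks, with the same tolerance and independent of dosing. SAP 4.1.2 agrees: "The first on-study tumor assessment is scheduled to be conducted at 6 weeks" after first dose, give or take a week. SAP 2.1 (Treatment Phase) has dosing start within 3 calendar days of randomization, and SAP 4.1.1 measures survival from randomization.

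A related table in SAP 7.5.2.10, repeated in 7.5.3.9, uses similar time points: "Cumulative Response Rates will be tabulated for Week 6, Week 12, Months 4, 6, 8, and 12".

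**The concern.** A landmark analysis works best when the status it splits on is settled at the landmark. Here the three early landmarks fall where the scan that decides the status may or may not have been done. Take two compliant subjects dosed on the day of randomization, with the same tumor response, one scanned on day 40 and the other on day 44. The first is a responder at the Week 6 landmark and the second is a non-responder.

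Moving true early responders into the non-responder group pulls the two survival curves together, so the early curves would understate any link between response and survival. The Week 6, Week 12 and Month 4 cumulative response rates are cut inside the same windows, so they read low against the scan then due.

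**Working it through.** The plan gives no figure for this analysis, so there is none to reproduce.

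**Inputs.** Scan *k* (up to Week 48) is due 42*k* days after first dose, ± 7 days (Protocol 5.4). The lag *d* from randomization to first dose is 0 to 3 days (SAP 2.1). One month is 30.4375 days (SAP Section 9). *Assumptions:* a response is dated by its scan, the clock starts at randomization, and the scan deviation *w* runs over whole days from −7 to +7. If the clock starts at first dose, use *d* = 0.

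**Step 1: overlap.** On-schedule scan days after randomization run from 42*k* − 7 to 42*k* + 7 + 3.

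- Scan 1: days 35–52; landmark Week 6 = day 42, inside.
- Scan 2: days 77–94; landmark Week 12 = day 84, inside.
- Scan 3: days 119–136; landmark Week 18 = day 126, inside.
- Month 6 = 6 × 30.4375 = day 182.6, between the Week 24 window (161–178) and the Week 30 window (203–220).
- Month 9 = day 273.9, between the Week 36 window (245–262) and the Week 42 window (287–304).
- Month 12 = day 365.25, between the Week 48 window (329–346) and the Week 60 window (413–430).
- Month 4 (response tables only) = day 121.75, inside the Week 18 window for lags of 0 to 2 days. With a 3-day lag that window opens on day 122.

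This step needs no assumption about when scans are actually done.

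**Step 2: share classed as non-response.** Reading *before* strictly, a response first seen at scan *k* is missed when 42*k* + *w* + *d* ≥ 42*k*, that is, when *w* ≥ −*d*. Under uniform timing the share is (8 + *d*)/15: 8/15 = 53%, 9/15 = 60%, 10/15 = 67% and 11/15 = 73% for *d* = 0, 1, 2 and 3.

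| Assumed timing in the window | *d* = 0 | *d* = 3 |
|---|---|---|
| Uniform | 53% | 73% |
| Triangular around the nominal day | 56% | 84% |
| Normal, SD 3 days | 57% | 88% |
| Skewed early (linear) | 30% | 55% |
| Skewed late (linear) | 77% | 92% |
| All on the nominal day | 100% | 100% |

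If *before* were read as on or before, the condition is *w* > −*d*. Uniform timing then gives 7/15 = 47% to 10/15 = 67%, early-skewed timing gives 23% at *d* = 0, and scans all on the nominal day with *d* = 0 give 0%.

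**Step 3: which responses are affected.** At Week 6 every known response comes from scan 1, so the share applies to all of them. At Weeks 12 and 18 it applies only to responses first seen at that scan. Responses from earlier scans are already classed correctly, and missed ones are picked up at the next landmark.

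**Step 4: response date.** Protocol 5.4 requires confirmation at least 4 weeks later. If the confirmation date counted, the earliest on-schedule responder would appear on day 35 + 28 = 63, after the Week 6 landmark and also after day 56.

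**Step 5: later landmarks.** One week later (Weeks 7, 13 and 19) leaves *w* ≥ 7 − *d* under uniform timing: 1/15 = 6.7% at *d* = 0 and 4/15 = 26.7% at *d* = 3. Two weeks later (days 56, 98 and 140) leaves none, because the last on-schedule scans are on days 52, 94 and 136.

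**The case against.** The strongest reply is that a landmark analysis is meant to condition on what is known at the landmark, and the SAP says so. A response documented on day 44 was not known on day 42, so classing that subject as a non-responder follows the method. This stands as far as validity goes: the placement of the landmarks creates no immortal-time bias. It does not remove the dilution, which comes from putting the cut where knowledge of response depends on the scan date.

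A second reply also stands. Six landmarks are planned and three are clean; the analysis is descriptive and sits outside the testing hierarchy in SAP 7.5.1. The response tables also come with the full curve and the overall rate, so no response is lost.

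A reader might infer more than the documents support:

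- *That about half of these responses are lost.* No scan-day distribution is given, so any single share is an assumption.
- *That early status reflects punctuality rather than tumor response.* This goes too far at Weeks 12 and 18, where earlier responses are classed correctly.
- *That differences in timing between arms would appear as differences in response.* The imaging schedule is the same in every arm, the landmark curves are drawn within arm, and the planned response-rate comparison uses no landmark. Nothing in the documents points to such a difference.

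**Conclusion.** The overlap follows from the documents alone: the Week 6, 12 and 18 landmarks lie inside the scan windows, whether the clock starts at randomization or at first dose. The size does not follow from them. With strict *before* and uniform scan days, 53% to 73% of the responses first seen at that scan are classed as non-response; the other timings tried give about 30% to 100%. The effect is worst at Week 6 and limited to newly seen responses at Weeks 12 and 18. Months 6, 9 and 12 are clear.

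The consequence is a diluted responder/non-responder contrast at the early landmarks and low early entries in the cumulative-response tables. This is a minor point, worth making because it is cheap to correct.

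**What to change.** In SAP 7.5.2.8 and 7.5.3.4:

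- Set the early landmarks at Weeks 8, 14 and 20 (days 56, 98 and 140) and keep Months 6, 9 and 12.
- State that the clock starts at randomization.
- State that a response counts from the date it was first documented, provided it is later confirmed, and not from the confirmation date. Without this, Week 8 could still precede every qualifying date (Step 4).

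In SAP 7.5.2.10 and 7.5.3.9, tabulate cumulative response at Weeks 8, 14 and 20 in place of Week 6, Week 12 and Month 4.

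The cost is SAP wording and a program parameter, plus a few more early deaths excluded before the later landmarks. Requiring later confirmation also uses some information from after the landmark, since a responder must live to be confirmed; the SAP should acknowledge this.

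Timing matters too. The SAP document history says version 5.0 followed the nivolumab plus chemotherapy analysis, for which the report had been written. For that comparison the revised landmarks should be shown as a supplementary analysis beside the planned ones. SAP Section 10 places the nivolumab plus ipilimumab report at the second time point, so 7.5.3.4 could be changed before that analysis.
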